## **3. PROTOCOL ABSTRACT**

| Sponsor:                     | Investigational Product: | Study Phase: |
|------------------------------|---------------------------------|--------------|
| Immunovative Therapies, Ltd. | AlloStim ®           | Phase IIA    |

#### **Study Title:**

In-Situ Cancer Vaccine: Phase IIA, Open-Label Study to Assess the Safety of AlloStim® in Combination with Cryoablation as Third Line Therapy for Metastatic Colorectal Cancer

#### Protocol Number:

ITL-019-CORK-CRYVAC

#### **Study Phase:**

Phase IIA

#### Indication:

Metastatic colorectal cancer third line therapy

## CryoVaxTM:

CryoVaxTM is the name provided by the Sponsor to protocols that incorporate an in-situ vaccination step. This protocol includes an in-situ cancer vaccine step, which combines a percutaneous ablation of a single metastatic tumor lesion with intralesional immunotherapy serving as an adjuvant. In this protocol, the ablation step is conducted using a percutaneous cryoablation procedure (CA). The ablation of the selected tumor lesion causes release of tumor-specific antigens into the microenvironment (antigen source) and the intralesional immunotherapy serves as an adjuvant to promote maturation of dendritic cells (DC) that engulf and process released tumor antigens. The mature DC migrate to the draining lymph nodes to elicit a Th1-type tumor-specific immune response. The combination of ablation and intralesional immunotherapy thus creates an in-situ, patient-specific, anti-tumor vaccine.

Some subjects enrolled in this study are scheduled to undergo cryoablation, while other subjects are scheduled to receive IV doses to try to create an in-vivo, patient-specific, anti-tumor in-situ vaccine.

## T-StimTM:

T-StimTM cells are an intermediate product in the process of making the study drug called AlloStim®. T-StimTM is ex-vivo differentiated and expanded memory CD4 T-cells that uniquely function as both Th1 cells (produce IFN-gamma and not IL-4) and natural killer cells (contain granzyme B and perforin and lyse tumor cells and not normal cells in-vitro). T-StimTM cells are derived from the blood of normal donors (allogeneic) and are intentionally mismatched to the recipients. The T-StimTM production process involves first purifying CD4+ T-cells from buffy coat material collected from known normal screened blood donors. The CD4+ cells are cultured in the presence of Dynabeads® ClinExVivo™ CD3/CD28 beads for 9 days. After the 9-day culture process, the CD4+ cells expand approximately 50-fold and differentiate into T-StimTM memory CD4 cells with Th1 and NK-like properties. The T-StimTM cells are harvested from the culture, washed, the beads are removed and the cells are aliquoted into individual dose vials. The dose vials are stored frozen in liquid nitrogen. Frozen T-StimTM doses are stable for at least 18 months. T-StimTM cells are produced in Jerusalem, Israel under cGMP and are certified USP sterile and low endotoxin (validated gel clot method) before release. All blood donors are screened pursuant to 21 CFR 1271 and tested to be free from blood-borne infectious diseases pursuant to US regulations (HIV1,

HIV2, HTLV1, HTLV2, HBV, HCV, syphilis, and additionally screened for CMV. Each batch is also tested to meet pre-determined identity and functional requirements prior to release.

## AlloStim®:

AlloStim® is formulated T-StimTM cells that have been activated by adding CD3/CD28conjugated microbeads and packaged in a syringe. AlloStim® is prepared by thawing frozen, QC released T-StimTM cells and incubating the cells for 4 hours with Dynabeads® *ClinExVivo*TM CD3/CD28. The beads are mixed with the cells at a 2:1 bead to cell ratio. After 4 hours, the cells with the beads attached are harvested, washed and suspended in formulation buffer containing PlasmaLyteA® supplemented with 1% human serum albumin. The formulated cells with the beads still attached are then loaded in a syringe for infusion or injection. A sample from the syringe lot is tested for bacterial contamination with a Rapid Microbiological Method (RMM) with results at 24 -48 hours. AlloStim® syringes are packaged in validated temperature-controlled containers and shipped by specialized courier service to the study site at least 48 hours prior to the protocol required treatment day for each enrolled subject. The syringe lots are quarantined at the study site until notification of RMM release. The cells are stable for at least 72 hours in this final formulation. AlloStim® is available in the following dosage forms:

- 1 ml formulation buffer containing 1 x 10^7 cells with 2 x 10^7 beads attached in a 3 ml syringe for intradermal injections (ID) and intratumoral (IT) injection,
- 3 ml formulation buffer containing 3 x 10^7 cells with 6 x 10^7 beads attached in a 10 ml syringe for intravenous injection (IV) and intratumoral (IT) injection,
- 5 ml of formulation buffer containing  $5 \ge 10^7$  cells attached to  $1 \ge 10^8$  beads in a 10 ml syringe for intravenous infusion (IV).

Note: some cohorts call for a 0.5 ml intradermal dose. For these cohorts, a 1 ml syringe will be provided and the clinic is instructed to administer only 0.5 ml and discard the remaining 0.5 ml.

## **Study Purpose:**

This is a Phase IIa open label, study designed to compare AlloStim+cryoablation vs AlloStim alone

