## **Dosing Schedule A-1: Treatment With Cryoablation**

The priming step: Subjects will receive an ID injection of AlloStim® (0.5 ml) on Days 0, 7, and 14 all in different locations.

The vaccination step: Subjects will receive cryoablation and intratumor (IT) injection of AlloStim® (1 ml) on Day 21.

The activation step: Subjects will receive an IV infusion of AlloStim® (3ml) on Day 28.

The booster step: Subjects will receive two (optional) IV booster infusions of AlloStim® (3ml), one on Day 56, a second on Day 84.

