# 7. STUDY OBJECTIVES

#### 7.1. PRIMARY OBJECTIVES

- 1. To determine the safety of AlloStim® combined with cryoablation vs AlloStim® alone.
- 2. Determine the schedule that provides the greatest efficacy and least adverse events

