# 8. STUDY DESIGN

This is a single center, open label study of CryoVaxTM personalized anti-tumor vaccine protocol combining the cryoablation of a selected metastatic lesion with intra-lesional immunotherapy compared to AlloStim® alone.

# Part 1

3 subjects will be accrued sequentially into schedule A-1 and A-2 (Part 1). After accrual of 6 subjects, up to 25 additional subjects will be accrued into the most favorable schedule (Part 2)

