### Dosing Schedule A-1: Intradermal and Intravenous Dosing Combined With Cryoablation

The priming step: Subjects will receive an ID injection of AlloStim® (0.5ml) on Days 0, 7, and 14 all in different locations.

The vaccination step: Subjects will receive cryoablation and intratumor (IT) injection of AlloStim® (3 ml) on Day 21.

The activation step: Subjects will receive an IV infusion of AlloStim® (3ml) on Day 28. The booster step: Subjects will receive two (optional) IV booster infusions of AlloStim® (5ml), one on Day 56 and Day 84.

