# Dosing Schedule A-2: Intradermal and Intravenous Dosing With AlloStim® alone

The priming step: Subjects will receive an ID injection of AlloStim® (0.5 ml) on Days 0, 3, 7, 10 and 14.

The vaccination step: Subjects will receive IV AlloStim® (3 ml) on Day 21.

The activation step: Subjects will receive an IV infusion of AlloStim® (3ml) on Day 28.

The booster step: Subjects will receive two IV booster infusions of AlloStim® (3ml), one on Day 49 and another on Day 77.

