# **16. STATISTICAL METHODS**

#### **16.1.** GENERAL CONSIDERATIONS

The Phase I/IIb study is primarily designed to assess the safety and tolerability of the study drug dosing schedule and the related immune response. Any evidence of clinical objective anti-tumor activity and/or symptomatic changes will be recorded.

Safety analyses will be performed on all subjects who receive any dose of study medication. All summary data will be presented by dosing schedule (Schedule A-1 vs Schedule A-2 vs. Schedule A-3 vs. Schedule A-4 vs. Schedule B vs. Schedule C vs. Schedule D vs. Schedule E vs. Schedule F). Any evidence of clinical objective anti-tumor activity and/or symptomatic changes will be recorded.

Descriptive statistics and/or subjects' listings will be provided for demographic data, incidence of adverse events (overall, by intensity, and by relationship to study medication), incidence of clinically significant laboratory abnormalities, vital signs, medical history and physical exam, and tumor assessments.

If subjects are administered steroids, the subject data will be censored at the date of steroid administration.

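### A-1 versus A-2 compares two whole schedules and cannot show what cryoablation adds; the by-schedule tables should also keep Part 1 apart from Part 2

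*Combined protocol and SAP*

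**What the plan says.** The abstract's Study Purpose describes a "study designed to compare AlloStim+cryoablation vs AlloStim alone". The abstract's brief description and Section 8 frame the study in the same way, and primary objective 1 (Section 7.1) is the safety of the combination against the drug by itself. Primary objective 2 is different: "Determine the schedule that provides the greatest efficacy and least adverse events".

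In Section 8, A-1 primes intradermally "on Days 0, 7, and 14 all in different locations", then gives cryoablation plus intratumoral drug on Day 21, an IV dose on Day 28 and optional boosters on Days 56 and 84. A-2 primes "on Days 0, 3, 7, 10 and 14", gives IV drug on Day 21 and again on Day 28, and has boosters "one on Day 49 and another on Day 77". The abstract's brief description presents the Day 21 IV dose in A-2 as the replacement for cryoablation.

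Part 1 takes three subjects per schedule, accrued sequentially. After that, "up to 25 additional subjects will be accrued into the most favorable schedule (Part 2"). Section 8 says Part 1 safety and efficacy data decide which schedule advances, but gives no criterion. On reporting, Section 16.1 says "All summary data will be presented by dosing schedule", and Section 16.1.6 includes everyone who received study drug. Neither mentions a split between Part 1 and Part 2.

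**The concern.** Two separate things can mislead a reader of the results.

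First, the stated purpose invites attribution of any A-1/A-2 difference to cryoablation. A-2 is not A-1 with the Day 21 step exchanged. The extra intradermal doses and shifted booster days touch the primary endpoint, because acute dose-limiting toxicity is assessed within 48 hours of each dose through the activation step, and the Safety Evaluation Period runs to 28 days after the last dose.

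Second, a schedule chosen because its first few subjects did well, and then enlarged, will tend to look better in a by-schedule table than the schedule left behind. The rejected schedule keeps its small, possibly unlucky cohort, while chance in the selected cohort is diluted by new subjects.

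**Working it through.** **Schedules side by side** (abstract, Section 8 and Tables 1 and 2 agree on these days)

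| | A-1 | A-2 | Declared as the contrast? |
|---|---|---|---|
| Intradermal days | 0, 7, 14 (3 doses) | 0, 3, 7, 10, 14 (5 doses) | No |
| Day 21 | Cryoablation + intratumoral | IV | Yes |
| Day 28 | IV | IV | Same |
| Booster days | 56, 84 | 49, 77 | No |

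Consequences, if both boosters are given:
- Doses through Day 28, each opening a 48-hour acute-toxicity window: 3 + 1 + 1 = 5 against 5 + 1 + 1 = 7. The whole difference comes from the two extra intradermal doses.
- End of the Safety Evaluation Period: 84 + 28 = Day 112 against 77 + 28 = Day 105.
- Day 91 CT and biopsy after the last dose: 91 − 84 = 7 days against 91 − 77 = 14 days.

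**Passages that disagree with this table**
- Section 14.4.1 lists four intradermal days for A-1 (0, 7, 14, 21) and three for A-2 (0, 7, 14). On that text, doses through Day 28 are 4 + 1 + 1 = 6 against 3 + 1 + 1 = 5, the opposite direction.
- The abstract announces three boosters for A-2 but lists two days.
- Volumes conflict. Abstract: A-1 3×0.5 + 1 + 3 + 2×3 = 11.5 ml; A-2 5×1 + 3 + 3 + 2×3 = 17 ml. Section 8: A-1 3×0.5 + 3 + 3 + 2×5 = 17.5 ml; A-2 5×0.5 + 3 + 3 + 2×3 = 14.5 ml. Even the sign of the total-dose difference depends on the section read.

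**Sample size.** Section 16.1.8 says at least 3 subjects per schedule, with no rate, alpha or power, so there is no calculation to reproduce. For scale, the most extreme 3 v 3 result (0/3 v 3/3) has a two-sided Fisher exact p of 2/20 = 0.10.

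**Selection illustration.** Table sizes as written: 3 + 25 = 28 against 3, if neither cohort is expanded under the 3+3 rule. Assumptions, none from the documents: both schedules have the same true rate p of some unfavorable event, the schedule with fewer events in its 3 subjects is chosen, ties are broken at random, and all 25 are accrued.

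Let D = E|X₁ − X₂|/3, with X₁ and X₂ independent Binomial(3, p). Then:
- rejected schedule: p + D/2
- selected schedule, Part 1: p − D/2
- selected schedule, pooled: [3(p − D/2) + 25p]/28 = p − 3D/56
- expected gap: D/2 + 3D/56 = 31D/56

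| p | D | Rejected (n=3) | Selected, pooled (n=28) | Gap, points |
|---|---|---|---|---|
| 10% | 0.151 | 17.5% | 9.2% | 8.3 |
| 20% | 0.234 | 31.7% | 18.7% | 13.0 |
| 30% | 0.281 | 44.0% | 28.5% | 15.5 |
| 40% | 0.305 | 55.2% | 38.4% | 16.9 |
| 50% | 0.313 | 65.6% | 48.3% | 17.3 |
| 60% | 0.305 | 75.2% | 58.4% | 16.9 |

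If the event is a dose-limiting toxicity, the upper rows are implausible. The 33% discontinuation rule (Sections 8 and 15.7) is met by 2 of 6 Part 1 subjects, with probability 1 − (1−p)⁶ − 6p(1−p)⁵: 77% at p = 40% and 96% at p = 60%. The trial would seldom reach Part 2.

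**The case against.** The best defense is that the plan already asks the whole-schedule question. Primary objective 2 is exactly that, Section 6.8.1 speaks of evaluating different schedules, and nothing promises an isolated estimate of what cryoablation contributes. This stands: objective 2 is not defeated by the differences above. It does not rescue the Study Purpose or objective 1, which name cryoablation as the contrast.

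The Day 21 difference is also the declared substitution, so the missing intratumoral dose and the additional IV dose should not be counted as confounding. That stands too. What remains is the intradermal count and the booster days.

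A reader might infer that A-2 carries more doses whichever section governs. Section 14.4.1 contradicts this. It also names schedules that the current design does not have and may be carried-over text, but it is in the document.

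A reader might also infer that the plan commits to pooling. It does not say so. Section 8 gives Part 1 its own completed safety evaluation, cohort safety reports are mentioned, and Section 15.3.2 has a submission at the end of Part 1. The A-1/A-2 decision itself therefore rests on Part 1 data. The 28 v 3 table follows only from Section 16 being silent on a split, and the rejected cohort could be 6 after 3+3 expansion.

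Finally, the analysis is descriptive, so no error rate or power is affected.

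**Conclusion.** The point holds in a limited form. Under the abstract, Section 8 and Tables 1 and 2, the A-1/A-2 contrast mixes cryoablation with two extra intradermal doses and different booster days. With sequential, non-randomised cohorts of three as well, it supports no conclusion about cryoablation itself. Dose counts should not be quoted as settled until Section 14.4.1, the A-2 booster count and the volumes are reconciled.

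The reporting point is a gap in Section 16.1 rather than a stated intention to pool. The expected spurious gap of about 8 to 16 points at rates of 10% to 30%, and about 17 at 40% to 60%, is an illustration that rests on an assumed selection rule, equal true rates and unexpanded cohorts. It shows direction and rough scale; it is not a prediction for this trial. For a small descriptive study this should be fixed, but it does not block the design.

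**What to change.** 1. Restate the Study Purpose, the abstract's brief description and objective 1 in Section 7.1 as a descriptive comparison of two complete schedules. Add that no conclusion about the contribution of cryoablation will be drawn. Leave objective 2 as it is.
2. Reconcile the intradermal days, the A-2 booster count and the volumes across the abstract, Section 8 and Section 14.4. Which text governs is for the sponsor and the investigator to settle.
3. In Section 16.1, take the A-1 v A-2 table from Part 1 subjects only, report Part 2 separately as the main estimate for the favored schedule, and show pooled figures as supportive. The full safety listing still covers every treated subject.

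The cost is wording and table shells, with a narrower claim. Leaving the three Part 1 subjects out of the main estimate raises its standard error by √(28/25) = 1.058, about 6%, if 25 are accrued. Part 2 is only a maximum of 25; if 10 are accrued, the factor is √(13/10) = 1.140, about 14%.

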## **Brief Description of the Protocol:**

This is a single center, open label study comparing CryoVaxTM personalized anti-tumor vaccine protocol combining the cryoablation of a selected metastatic lesion with intra-lesional immunotherapy with AlloStim® alone. The treatment schedules both have the following steps: (1) priming with intradermal AlloStim®; (2) vaccination combining cryoablation with intratumoral AlloStim® or intravenous AlloStim® dosing in the place of cryoablation; (3) activation with intravenous AlloStim®; and (4) booster with intravenous AlloStim®. All subjects are followed for safety during the dosing period and until 28 days following the last dose (Safety Evaluation Period"). All subjects are continued to be followed for survival after the Safety Evaluation Period.

## **Dosing Schedule A-1: Treatment With Cryoablation**

The priming step: Subjects will receive an ID injection of AlloStim® (0.5 ml) on Days 0, 7, and 14 all in different locations.

The vaccination step: Subjects will receive cryoablation and intratumor (IT) injection of AlloStim® (1 ml) on Day 21.

The activation step: Subjects will receive an IV infusion of AlloStim® (3ml) on Day 28.

The booster step: Subjects will receive two (optional) IV booster infusions of AlloStim® (3ml), one on Day 56, a second on Day 84.

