#### 14.4.2. Intravenous Infusions (IV)

Schedules A-1 and A-2: Each IV push contains  $3 \times 10^7$  AlloStim® cells formulated in 3 ml of 1% human serum albumin in PlasmaLyteA. Pre-formulated 10 ml syringes of AlloStim® will be delivered to the study site on or prior to the IV administration day. AlloStim® is administered as an IV push over approximately 5 minutes.

Subjects may be hydrated with 500 - 2000 ml of NS (or similar) prior to infusion and may be medicated with 25-50 mg diphenhydramine PO/IV, 150 mg ranitidine (Zantac) PO or other H-2 blocker, 25-50 mg PO indomethacin (or equivalent NSAID) during or after the infusion if medically indicated.

After each IV administration of study drug, the vital signs will be monitored manually every 15 minutes or with real-time monitoring equipment for heart rate, respiration rate, blood pressure, temperature, and pulse oximetry. Values will be recorded prior, during and for 2 hours following the infusion. All changes in vital signs from baseline during and after the infusion will be recorded in the treatment notes.

The physician on duty has the authority to stop, delay, or cancel the infusion at any time if medically indicated. Any such actions that deviate from the infusion protocol will be recorded in the treatment notes and appropriate CRF or eCRF.

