# 14.4.3. Intratumoral Injections (IT)

Subjects in schedule A-1 will receive an IT injection of AlloStim® (3 ml) on Day 21 into the same ablated lesion on Day 17.

Each IT injection contains either  $1 \ge 10^7$  AlloStim® cells formulated in 1 ml or  $3 \ge 10^7$  AlloStim® cells formulated in 3 ml of 1% human serum albumin in PlasmaLyteA. Preformulated 3 or 10 ml syringes of AlloStim® will be delivered to the study site on or prior to the IT administration day.

After each IT administration of study drug the vital signs will be monitored with real-time monitoring equipment for heart rate, respiration rate, blood pressure, temperature, and pulse oximetry. Values will be recorded every 15 minutes prior, during and for 2 hours following the administration. All changes in vital signs from baseline during and after the administration will be recorded in the treatment notes.

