## **19. APPENDICES**

#### **APPENDIX 1** BIOPSY, CRYOABLATION SURGICAL PROCEDURE

Subjects will be referred to a sponsor dedicated radiology center for the cryoablation and voluntary biopsy procedures and intratumoral injections.

Preferably, the lesion selected for biopsy will not be the same lesion as is targeted for ablation. However, if a second lesion is not available then the lesion for ablation will be biopsied prior to ablation. The cryoablation and biopsy procedures are conducted under CT and/or ultrasound guidance. Visual documentation of probe placement for the cryoprobe probe will be provided and placed in the source documents. In addition, visual documentation of the kill zone after the ablation will also be provided for cryoablation. The tumor biopsy specimen will be placed in formalin in a pre-labeled specimen container. The tumor biopsy specimen will be sent to the Sponsor for pathological analysis.

Subjects will have a target tumor lesion cryoablated under local or conscious sedation followed by an intratumoral AlloStim® injection at a dose of  $1 \times 10^7$  cells formulated in 1 ml of Plasma-LyteA/1% HAS or  $3 \times 10^7$  cells formulated in 3 ml of Plasma-LyteA/1% HSA. The intent of the ablation procedure is not to completely ablate the target lesion, but only to cause an area of necrosis within the tumor. Therefore, it is not necessary to have perfect margins. The intratumoral injection will occur after the ablation area has warmed to  $37^{\circ}$ C.

It is preferred that an interventional radiologist, CT technician, and physician trained in anesthesia or emergency medicine be present during the procedure. A Registered Nurse (RN), medical assistant and a cryoablation technician should also be present to support these procedures (same individual may function in two of these roles). The Sponsor may also have a medical/scientific consultant present. If the ablation target is in or near the lungs, it is recommended that the procedure be conducted in a hospital or near a hospital with the capability to diagnose and treat pneumothorax or related complications.

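### Three doses differ between Sections 3, 8 and 14 and nothing says which governs, so the two regimens under the primary safety endpoint are not uniquely defined

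*Combined protocol and SAP*

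**What the plan says.** **A-1 intratumoral dose.** Section 3: "Subjects will receive cryoablation and intratumor (IT) injection of AlloStim ® (1 ml) on Day 21". Section 8: "Subjects will receive cryoablation and intratumor (IT) injection of AlloStim ® (3 ml) on Day 21". Section 14.4.3 assigns A-1 3 ml, but places it "on Day 21 into the same ablated lesion on Day 17", although ablation is on Day 21 everywhere else for this schedule. The next paragraph of 14.4.3 describes both a 1 ml and a 3 ml injection. Appendix 1 does the same: 1 × 10^7 "cells formulated in 1 ml of Plasma-LyteA/1% HAS or" 3 × 10^7 cells in 3 ml.

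**A-1 boosters.** Section 3: "Subjects will receive two (optional) IV booster infusions of AlloStim ® (3ml), one on Day 56, a second on Day 84". Section 8: "Subjects will receive two (optional) IV booster infusions of AlloStim® (5ml), one on Day 56 and Day 84". Section 14.4.2 gives each IV push for A-1 and A-2 as 3 × 10^7 "cells formulated in 3 ml of 1% human serum albumin in PlasmaLyteA. Pre-formulated 10 ml syringes". Section 14.1 lists only a 3 ml IV syringe, but the dosage forms in Section 3 include one of "5 ml of formulation buffer containing" 5 × 10^7 cells.

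**A-2 intradermal dose.** Section 3 gives 1 ml on Days 0, 3, 7, 10 and 14. Section 8 gives 0.5 ml on the same days. Section 14.4.1 gives 0.5 ml for both schedules, with the other 0.5 ml discarded. It also puts 1 × 10^7 cells in 0.5 ml, whereas Sections 3 and 14.1 put 1 × 10^7 cells in 1 ml.

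**A-2 boosters.** Section 3 announces three optional boosters and dates two (Days 49 and 77). Section 8 has two and does not call them optional. Table 2 in Section 12 shows two.

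**The concern.** Safety is the primary endpoint (Section 9.1), and these figures define the two regimens being assessed. The intratumoral and intradermal conflicts fall in the priming and vaccination steps, where the 3+3 rule counts acute dose-limiting toxicity. That definition includes Grade 3 or worse injection-site reactions. The booster conflict falls in the period that counts toward cumulative toxicity and the 33% discontinuation rule. The favored schedule then goes to up to 25 more subjects (Section 8). If its doses are not fixed, the regimen carried forward, and the one the safety conclusion describes, cannot be read from the protocol.

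**Working it through.** **1. The sections side by side (dose volumes, ml)**

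| Dose | Section 3 | Section 8 | Section 14 |
|---|---|---|---|
| A-1 intratumoral | 1 | 3 | 3 (then either form described) |
| A-1 booster, each | 3 | 5 | 3 |
| A-2 intradermal, each | 1 | 0.5 | 0.5 |

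At least two of the three sections agree on each dose, but not the same two each time. Section 14 sides with Section 8 on the first and third rows and with Section 3 on the second. No order of precedence is stated.

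**2. Size of each conflict**, at 1 × 10^7 cells per ml (Sections 3 and 14.1):
- A-1 intratumoral: 3/1 = 3-fold.
- A-1 booster: 5/3 = 1.67-fold each; 2 × 3 = 6 or 2 × 5 = 10 (× 10^7) if both are given.
- A-2 intradermal over five injections: 5 × 1 = 5.0 or 5 × 0.5 = 2.5 (× 10^7), 2-fold.

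**3. Totals over the 3+3 steps** (priming + vaccination + activation, × 10^7 cells). The undisputed doses are A-1 intradermal 0.5 ml × 3, A-2 Day 21 IV 3 ml, and Day 28 IV 3 ml in both schedules.
- Section 3: A-1 = 3 × 0.5 + 1 + 3 = 5.5; A-2 = 5 × 1 + 3 + 3 = 11.0; A-2/A-1 = 2.00.
- Section 8: A-1 = 3 × 0.5 + 3 + 3 = 7.5; A-2 = 5 × 0.5 + 3 + 3 = 8.5; A-2/A-1 = 1.13.
- Section 14 volumes on the Section 3 and 8 days: 7.5 and 8.5 again.

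**4. Sensitivity to the intradermal cell content.** Section 14.4.1 read literally puts 1 × 10^7 cells in each 0.5 ml injection. Section 14 then gives A-1 = 3 × 1 + 3 + 3 = 9.0 and A-2 = 5 × 1 + 3 + 3 = 11.0, a ratio of 1.22. On that reading A-2 intradermal is 5.0 × 10^7 at either volume, and the 2-fold difference in cells disappears. The instruction to discard half of the 1 ml syringe points the other way, to 0.5 × 10^7 per injection. The cell dose is therefore unclear as well as the volume.

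**5. Adding the two dated boosters** (× 10^7 cells, 1 × 10^7 per ml):
- Section 3: A-1 = 5.5 + 6 = 11.5; A-2 = 11.0 + 6 = 17.0.
- Section 8: A-1 = 7.5 + 10 = 17.5; A-2 = 8.5 + 6 = 14.5.
- Section 14 volumes: A-1 = 7.5 + 6 = 13.5; A-2 = 8.5 + 6 = 14.5.

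The schedule with more drug changes from A-2 under Section 3 to A-1 under Section 8. The reversal depends on Section 8's 5 ml booster; with 3 ml boosters A-2 stays higher.

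**The case against.** **Section 14 is the operational text, so it governs.** Section 14 agrees with the majority on all three volumes, and 14.4.1 is explicit about the intradermal volume. That suggests the likely intent, but it is not a rule. Section 14 also has errors of its own: the Day 17 ablation, intradermal days that differ from Sections 3 and 8 for both schedules, and references to schedules this version does not define. The paragraph in 14.4.3 covering both intratumoral forms may only describe syringe contents, since the preceding one assigns 3 ml to A-1.

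**The 5 ml booster is a slip.** Probably. Section 8 is the only place that assigns it. It is not self-evidently an error, because Section 3 lists a 5 ml IV form.

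**Supply controls the dose.** This largely stands. The sponsor approves each subject's schedule and ships the product (Section 11.1), and IV and intratumoral doses arrive in pre-formulated syringes (14.4.2, 14.4.3). A reader might infer that subjects in one three-patient cohort will receive different doses and spoil the 3+3 count. The documents do not show that this is likely for IV or intratumoral dosing. The risk is greatest for the intradermal volume, which the site measures from a 1 ml fill. Consistent shipping would make dosing uniform, but it would not make the protocol state the dose.

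**Doses given are recorded and were used before.** Both are true. Administration details are captured (Sections 14.3 and 17.10.1). In the earlier study (Appendix 3, ITL-002-CRYO) the per-dose ranges were 1–4 intradermal, 1–6 intratumoral and 1–100 IV (× 10^7 cells). The variants here are 0.5–1, 1–3 and 3–5, all within or below those ranges. An inference that subjects face an untested high dose is not supported.

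**Conclusion.** The point holds as an undefined regimen. Three doses conflict in the current text by factors of 3, 1.67 and 2, the intradermal cell count is uncertain, and the A-2 booster count contradicts its own dates. Over the 3+3 steps the A-1 versus A-2 totals are 5.5 versus 11.0, 7.5 versus 8.5, or 9.0 versus 11.0 (× 10^7 cells), depending on the section followed and how 14.4.1 is read. The first two pairs assume 1 × 10^7 cells per ml, and all three use the dosing days of Sections 3 and 8. Sums across routes show how far the texts diverge. They are not an exposure measure, so a reader should not conclude that A-2 delivers twice the biological dose of A-1. No test, power or sample-size figure is affected. The protocol still cannot be followed as written on its central content, so this should be settled before dosing and is more than a clerical correction.

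**What to change.** Put one governing dosing table in the protocol giving, for each schedule and step, cells, volume, route, day, number of scheduled boosters and whether they are optional. Have Sections 3, 8, 12, 14 and Appendix 1 refer to it.

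The sponsor should confirm the values. The majority reading is intratumoral 3 ml, boosters 3 ml, intradermal 0.5 ml with the cell count stated, and two scheduled boosters. List separately the discretionary monthly boosters that Section 14.6 allows after the Study Period.

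In the same amendment, correct the Day 17 ablation in 14.4.3, the intradermal days and undefined schedules in 14.4.1, and the count of three A-2 boosters in Section 3. An extra safety table by dose received is not needed once the regimen is fixed.

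The cost is an amendment with IEC/IRB approval and possibly a revised consent form (Section 17.4), with no additional patients, visits or data.
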